## **Subjects who were partial responders at Week 52**

### **PASI 50, PASI 75, PASI 90, PASI 100 and IGA 0 or 1 response over time**

Summary statistics for PASI 50, PASI 75, PASI 90, PASI 100 and IGA 0 or 1 response by visit will be presented in contingency tables and will include absolute and relative frequencies. Confidence intervals for response rates will be derived as well based on the score method including continuity correction ([Newcombe, 1998](#)).

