#### Table 1-2Treatment groups by subjects group for efficacy analysis

Evaluation of	Analysis Period	Treatment group label (order as listed)	Analysis
Subjects who were PASI 75 responders at Week 52	RW	AIN457 150 mg  AIN457 300 mg  AIN457 150 mg – Placebo  AIN457 300 mg – Placebo 	PASI 50/75/90/100 response and IGA 0 or 1 response Loss of PASI 75/IGA 0 or 1 response Time to relapse DLQI
Subjects who were re-treated after relapse with AIN457 150 mg or 300 mg	Treatment	AIN457 150 mg Placebo - AIN457 150 mg  AIN457 300 mg Placebo - AIN457 300 mg 	PASI 50/75/90/100 response and IGA 0 or 1 response
All subjects	On Treatment Period	AIN457 150 mg stay  AIN457 300 mg stay  All AIN457 150 mg  All AIN457 300 mg  AIN457 150 mg only  AIN457 150 mg - 300 mg  AIN457 300 mg only 	Final analysis

 AIN457 150mg group includes the PASI 75 responders at week 52 who were randomized to AIN150mg at week 52; and the partial responders at week 52 were continued received AIN 150mg from week 52.

 AIN457 300mg group includes the PASI 75 responders who were randomized to AIN300mg at week 52; and the partial responders at week 52 were continued received AIN 300mg from week 52.

Novartis	Confidential	Page 12
RAP Module 3	9-Apr-2018 (1:15)	Secukinumab / AIN457A2302E1

 AIN457 150mg – Placebo group includes the PASI 75 responders who were assigned AIN 457 150mg during core study, and randomized to placebo at week 52.

 AIN457 300mg – Placebo group includes the PASI 75 responders who were assigned AIN 457 300mg during core study, and randomized to placebo at week 52.

 Placebo – AIN457 150mg group includes the subjects who were randomized to placebo at week 52, and relapsed then treated by AIN457 150mg during RW period.

 Placebo – AIN457 300mg group includes the subjects who were randomized to placebo at week 52, and relapsed then treated by AIN457 300mg during RW period.

 AIN457 150 mg stay group includes the subjects who were PASI 75 responders at Week 52 and staying strictly in 150 mg AIN457 treatment from Week 52. The subjects received placebo at Week 52 and switched to AIN457 150 mg will not be included in this treatment group. Subjects up-titrated from AIN457 150 mg to 300 mg during open label period will not be included in this group.

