 AIN457 300 mg stay group includes the subjects who were PASI 75 responders at Week 52 staying strictly in 300mg AIN457 treatment from Week 52. The subjects received placebo at Week 52 and switched to AIN457 300 mg will not be included in this treatment group.

 All AIN457 150 mg group includes all the subjects who were assigned to AIN457 150 mg at Week 52, regardless whether they are initial PASI 75 responder or partial responder at Week 52, or who were assigned to placebo at week 52 but relapsed and retreated by AIN457 150 mg during randomized withdrawal period. The subjects who up titrated to 300 mg during the open label period will be included in the efficacy analysis for this treatment group. For the subjects assigned to placebo group at Week 52 and switched to AIN457 150 mg after relapse, the efficacy data after 16 weeks (including 16 weeks) post AIN457 treatment will be included in this group. In addition, the subgroup analysis will be performed for the following two subgroup groups: 1) Subjects who stayed on AIN457 150mg and never were up-titrated; 2) Subjects up-titrated from AIN457 150mg to 300mg during open label period.

All AIN457 300 mg group includes all the subjects who were assigned to AIN457 300 mg at Week 52, regardless whether they are initial PASI 75 responder or partial responder at Week 52, or who were assigned to placebo at week 52 but relapsed and retreated by AIN457 300 mg during randomized withdrawal period. For the subjects assigned to placebo group at Week 52 and switched to AIN457 300 mg after relapse, the efficacy data after 16 weeks post AIN457 treatment will be included in this group. The subjects up titrated during the open label period will not be included in this group.

AIN457 150 mg only group is from 'ALL AIN457 150 mg' group and includes the subjects who were PASI 75 responders or partial responder at Week 52 and staying strictly in 150mg AIN457 treatment from Week 52. The subjects received placebo at Week 52 and switched to AIN457 150 mg will not be included in this treatment group. Subjects up-titrated from AIN457 150mg to 300mg during open label period will not be included in this group.

 AIN457 150 mg - 300 mg group is from 'ALL AIN457 150 mg' group and includes the subjects who started AIN457 150 mg from Week 52 and up-titrated from AIN457 150mg to 300mg during open label period.

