 AIN457 300 mg only group is from 'ALL AIN457 300 mg' group and includes the subjects who were PASI 75 responders or partial responder at Week 52 and staying strictly in 300mg AIN457 treatment from Week 52. The subjects received placebo at Week 52 and switched to AIN457 300 mg will not be included in this treatment group.

Evaluation of	Analysis Period	Treatment group label (order as listed)	Comment on treatment group definition	
Table/Figure	Entire stud Period, Follow-up Period	
 
y Any AIN 457 150 mg Any AIN 457 300 mg Any AIN 457 dose AIN 457 150 mg – Placebo AIN 457 300 mg – Placebo
 
2 Any AIN 457 150 mg Any AIN 457 300 mg Any AIN 457 dose
 
	Same as in Table 1-1 Same as in Table 1-1	

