For final analysis, the following treatment groups will be reported for the on treatment period.

AIN457 150 mg stay AIN457 300 mg stay All AIN457 150 mg All AIN457 300 mg AIN457 150 mg only AIN457 150 mg - 300 mg AIN457 300 mg only

The following study periods will be considered for analysis:

- Screening period (before Randomization in extension)
- **Randomized** withdrawal (RW) period for subjects who were PASI 75 responders at Week 52- the duration of RW period for each subject is different i.e., starting from Week 52 until the subject experiences the first full relapse for efficacy analyses and until the subjects reinitiating the secukinumab after first full relapse for safety analyses. RW period is not fixed for all the subjects but varies for subject to subject based on occurrence of relapse. Subjects not experiencing the relapse will end their RW period at Week 156.
- **Treatment** period for subjects with relapse (for efficacy analyses it is starting from the visit in RW period at which a subject experiences first full relapse to Week 156. Safety analysis will not be re-run for subjects with relapse).
- **Treatment** period for subjects with partial response (Week 52 to Week 156)
- **Open label** period for subjects who were continued in the study and were unblinded at Week 156. The first open label dose were given at the site at Week 156. Subjects previously randomized to receive 150 mg secukinumab may continue with 150 mg secukinumab open label or may switch to 300 mg s.c. at the discretion of the investigator. Subjects previously randomized to 300 mg secukinumab continued with 300 mg secukinumab open label. Placebo subjects who entered the open label period were given once weekly s.c. injections of secukinumab for 4 consecutive weeks and then s.c. injections every 4 weeks. Any subject starting on secukinumab 150 mg may continue on 150 mg every 4 weeks or switch to 300 mg at Week 156 or any other regular site visit if the investigator decided the subject would benefit from the higher dose. The Week 244 visit was the last scheduled visit at which the subjects were allowed to switch to 300 mg dose. Decreasing the dose from 300 mg to 150 mg was not allowed.
- Follow-up (FU) period (for all subjects)\*: treatment free period (Week 264 to Week 268).

Novartis	Confidential	Page 15
RAP Module 3	9-Apr-2018 (1:15)	Secukinumab / AIN457A2302E1

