- Follow-up 2 (FU 2) period: treatment free period only for subjects who prematurely discontinued treatment. All subjects who prematurely discontinued treatment should complete all assessment of Week 260 (end of treatment visit) and of the follow-up period visits (Weeks 264 and 268). Subsequently, adverse events and use of concomitant medication were evaluated by the investigator through telephone calls every 3 months for duration of 4 years from the time when subject has been enrolled into CAIN457A2302E1 study.
- Entire study period = Combination of RW period + treatment period for subjects with relapse and treatment period for subjects with partial response + open label period (Week 156 Week 260) + follow-up period (Week 264 Week 268).
- On treatment period = Combination of RW period + treatment period for subjects with relapse and treatment period for subjects with partial response + open label period (Week 156 Week 260).

The number of subjects in the analysis sets may differ between the study periods listed above.

The primary and secondary efficacy variables for final analysis are described as in table 1-4.

Endpoint/analysis	is Period					
	RW	treatment (re-treated after relapse)	treatment (partial responders)	On treatment period	Follow-up	Entire study period
Demography & baseline characteristics	Х					Х
Previous & concomitant medication						Х
Medical history						Х
Study medication: duration of exposure						Х
Loss of PASI 75 response over time after 52 weeks of treatment	Х					
PASI 50/75/90/100 and IGA mod 2011 0 or 1 response over time	Х	X 		Х		
Loss of IGA 0 or 1 response over time after 52 weeks of treatment	X 					

Table 1-4Analysis by period

Endpoint/analysis		Period				
	RW	treatment (re-treated after relapse)	treatment (partial responders)	On treatment period	Follow-up	Entire study period
PASI score over time				Х		
IGA mod 2011 score over time				Х		
Relapse					Х	
Rebound					Х	
EQ-5D				Х		
DLQI	Х			Х		
HAQ © -DI				X 		
DLQI 0 or 1 achievement	Х			Х		

X: for subjects who re-treated with secukinumab

X for subjects with PSA at baseline of the core study

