# 1.4 Subgroup definitions

No subgroup analyses will be conducted for final analysis.

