## 1.9.5 Secondary variables

Secondary variables are:

**PASI 50/75/90/100 and IGA mod 2011 0 or 1 response over time** in subjects who were PASI 75 responders at Week 52, over time for subjects who were re-treated after relapse with secukinumab 150 mg or 300 mg, and over time in subjects who were partial responders at Week 52.

Loss of PASI 75 response over time in subjects who were PASI 75 responders at Week 52

**Loss of IGA 0 or 1 response over time** in subjects who were PASI 75 responders as well as IGA 0 or 1 responders at Week 52

**PASI score over time** in subjects who were PASI 75 responders at Week 52, over time for subjects who were re-treated after relapse with secukinumab 150 mg or 300 mg, and over time in subjects who were partial responders at Week 52.

Novartis	Confidential	Page 46
RAP Module 3	9-Apr-2018 (1:15)	Secukinumab / AIN457A2302E1

**IGA mod 2011 score over time** in subjects who were PASI 75 responders at Week 52, over time for subjects who were re-treated after relapse with secukinumab 150 mg or 300 mg, and over time in subjects who were partial responders at Week 52.

**Relapse** in subjects who were PASI 75 responders at Week 52, over time for subjects who were re-treated after relapse with secukinumab 150 mg or 300 mg, and over time in subjects who were partial responders at Week 52.

**Rebound** in subjects who were PASI 75 responders at Week 52, over time for subjects who were re-treated after relapse with secukinumab 150 mg or 300 mg, and over time in subjects who were partial responders at Week 52.

**EQ-5D** in subjects who were PASI 75 responders at Week 52, over time for subjects who were re-treated after relapse with secukinumab 150 mg or 300 mg, and over time in subjects who were partial responders at Week 52.

**DLQI score as well as DLQI 0 or 1 achievement** in subjects who were PASI 75 responders at Week 52, over time for subjects who were re-treated after relapse with secukinumab 150 mg or 300 mg, and over time in subjects who were partial responders at Week 52.

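### The SAP's final analysis leaves out the separate partial-responder summaries that the protocol plans, and does not list this as a change

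*SAP*

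**What the plan says.** **Protocol.** Section 3.2 admits partial responders because continued treatment may still be worthwhile for them. Section 2.2 names them in seven objectives: PASI/IGA response, PASI/IGA score, safety, DLQI change, DLQI 0 or 1, EQ-5D and rebound. Section 9 lists them as an analysis population with a 150 mg and a 300 mg group. Section 9.5.1 has a block headed "Subjects who were partial responders at Week 52", covering response rates with confidence intervals, PASI score, IGA score, relapse and rebound.

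**SAP, variables.** Section 1.9.5 keeps the population, defining PASI/IGA response, PASI and IGA scores, relapse, rebound, EQ-5D and DLQI for PASI 75 responders, for re-treated subjects, "and over time in subjects who were partial responders at Week 52".

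**SAP, planned output.** Section 1.3 says "For final analysis, the following treatment groups will be reported for the on treatment period" and lists seven. By the footnotes to Table 1-2, they are made up as follows:
- The *stay* groups are PASI 75 responders only: "AIN457 150 mg stay group includes the subjects who were PASI 75 responders at Week 52".
- The *All* groups take subjects "regardless whether they are initial PASI 75 responder or partial responder at Week 52".
- The *only* groups also pool both kinds of responder, limited to those who kept a single dose throughout the extension.
- The *150 mg - 300 mg* group takes up-titrated subjects with no split by Week 52 response.

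Section 1.3 also says that "The primary and secondary efficacy variables for final analysis are described as in table 1-4". That table has a column for the partial responders' treatment period, which SAP 1.3 defines as Week 52 to Week 156. No row is marked in it. SAP 1.4 adds: "No subgroup analyses will be conducted for final analysis".

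**The concern.** The SAP defines secondary variables in a population and then plans no output for that population. Following it to the letter leaves the partial-responder part of seven secondary objectives unanswered in the final analysis. SAP 1.1.1, where departures from the protocol belong, does not mention it.

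What is at stake is whether subjects with an incomplete response at one year gain, hold or lose response on continued secukinumab. A pooled column answers that poorly. At Week 52 the PASI 75 rate is 100% in one component and 0% in the other by definition, so movement in the pooled rate can come from either. The *stay* groups show the PASI 75 responders on their own; nothing does the same for the partial responders.

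**Working it through.** **1. Structure, by counting**

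| Item | Count |
|---|---|
| Protocol 2.2 secondary objectives naming partial responders | 7 of 12 |
| Final-analysis groups that are partial responders alone (SAP 1.3) | 0 of 7 |
| Marks in the partial-responder column of Table 1-4 | 0 |
| Partial-responder rows in Table 1-2 | 0 |
| Partial-responder blocks in SAP 1.9.6 | 0 (blocks exist for the final analysis, the randomized withdrawal and re-treated subjects) |

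The five objectives that do not name them are time to PASI 75, loss of IGA 0 or 1, time to IGA 0 or 1, relapse and immunogenicity. The safety groups in Table 1-3 are also pooled regardless of response status. The blank column agrees with the text around it, so it is not an effect of text extraction.

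**2. The plan's own total, reproduced**

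Inputs: 414 PASI 75 responders per dose and a 65% PASI 75 rate at Week 52, stated for 150 mg (Protocol 9.7); a PASI 50 rate of about 95% and about 1,220 entrants (Protocol 4).

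- Completers per dose: 414 / 0.65 = 636.9
- Entrants: 2 x 636.9 x 0.95 = 1,210, against the stated 1,220 (0.8% apart)

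**3. Expected number of partial responders**

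- By difference: 1,220 - 2 x 414 = 392, and 392 / 1,220 = 32%
- From the rates: 636.9 x (0.95 - 0.65) = 191 per dose, about 382 in all
- Scaled to the 1,146 randomized (Amendment 2): 1,146 x 0.30 / 0.95 = 362
- If the PASI 75 rate were 80% in both doses (an assumption; no 300 mg rate is given): 1,146 x 0.15 / 0.95 = 181

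**4. Share of subjects on continuous secukinumab from Week 52, per dose, before up-titrated subjects are removed**

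- At 65%: 191 / (276 + 191) = 41%, so the pooled PASI 75 rate at Week 52 is 59%
- At 80%: PASI 75 responders on active drug are 636.9 x 0.80 x 2/3 = 339.7 and partial responders 636.9 x 0.15 = 95.5; 95.5 / 435.2 = 22%

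**5. What a pooled rate can show**

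With partial-responder share s = 0.409, pooled rate = s x q + (1 - s) x r, where q is the partial-responder rate and r the PASI 75-responder rate. A later pooled rate of 60% fits each of these:

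- q = 30%: r = (0.60 - 0.409 x 0.30) / 0.591 = 81%
- q = 45%: r = 70%
- q = 60%: r = 60%

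A pooled column alone therefore does not identify q.

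**6. What subtraction recovers**

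*only* minus *stay* leaves every partial responder on 300 mg, and on 150 mg those never up-titrated. Response variables are generally shown as observed case (SAP 1.9.4), so these counts would be exact. Up-titrated 150 mg partial responders stay merged with up-titrated PASI 75 responders in *150 mg - 300 mg*. Medians and quartiles, which SAP 1.1 requires for continuous variables, cannot be obtained by subtraction in either dose.

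**7. A related contradiction**

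Footnotes 1 and 2 of Table 1-2 put partial responders into the 150 mg and 300 mg groups of the row for PASI 75 responders in the randomized withdrawal period. Protocol 3.1 says that partial responders do not take part in the randomized withdrawal.

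**The case against.** The strongest reply is scope. SAP 1.1 says the document mainly covers the final analysis and that key analyses were conducted previously; SAP 1.9.1 says only part of the variables enter the final analysis. The empty column covers Weeks 52-156, so a blank may mean not re-run. This stands as a limit. A reader might infer that the partial responders' course is never reported except pooled; the documents do not support that. Nor do they cite an earlier report. They specify no other analysis of Weeks 156-260, although Protocol 9.6 allows further interim analyses.

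Second, Protocol 3.2 describes the open-label years as mainly for safety data, and 9.5.1 gives no end week for these summaries. That softens the commitment after Week 156. But the SAP does report PASI, IGA and DLQI over the whole on-treatment period for other groups, and the objectives say over time.

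Third, subtraction goes some way. It would be wrong to say that nothing can be recovered. But for 150 mg the recoverable part is selected, because up-titration is at the investigator's discretion, and no such output is planned.

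Fourth, SAP 1.4 is not a reliable prohibition: footnote 9 of Table 1-2 itself plans two subgroup analyses. Those split by up-titration, however, not by Week 52 response.

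Finally, footnotes 1 and 2 might suggest that the randomized comparison is contaminated. The row label, the SAP 1.9.6 heading and the risk set in SAP 1.9.7 all restrict it to PASI 75 responders, so this is a wording conflict to correct, not evidence of a biased test.

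**Conclusion.** The concern holds for the final analysis and for Weeks 156-260: a population named in seven of 12 secondary objectives has no planned output of its own, and the change is not declared. For Weeks 52-156 it holds only if no earlier report covers the group, which these documents cannot settle.

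The size is about 360 to 390 subjects (32% of entrants) at a 65% PASI 75 rate, falling to about 180 of 1,146 at 80%. As a share of those on continuous secukinumab from Week 52 that is about 41% down to 22%. This rests on applying a rate stated for 150 mg to both doses; the 80% is an assumption. The group is not negligible anywhere in that range.

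The primary endpoint and the testing strategy are untouched. These are descriptive summaries of a non-randomized group, so the change should be made but does not bear on the confirmatory result.

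**What to change.** 1. **Table 1-2.** Add a row for subjects who were partial responders at Week 52, with AIN457 150 mg and 300 mg by dose at Week 52, for the treatment period (Weeks 52-156). Add a separate on-treatment row to Week 260, with subjects up-titrated from 150 mg to 300 mg shown separately.
2. **Table 1-4.** Mark the partial-responder column (Weeks 52-156) for PASI 50/75/90/100 and IGA 0 or 1 response, PASI score, IGA score, DLQI, DLQI 0 or 1 and EQ-5D. Note that the on-treatment column is also shown for partial responders, except EQ-5D, which is not collected open-label, and that the follow-up relapse and rebound rows are too.
3. **SAP 1.9.6 and 1.4.** Add a matching method block to 1.9.6, and reconcile 1.4 with it and with footnote 9.
4. **Table 1-2, footnotes 1 and 2.** Remove partial responders, so that the randomized-withdrawal row holds PASI 75 responders only.

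If Weeks 52-156 have already been reported, cite that report in SAP 1.1.1 and add only the analysis to Week 260. Anything deliberately left out should be stated and justified in 1.1.1.

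The cost is SAP wording and extra columns in descriptive tables. No new data are needed.

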# 1.4 Subgroup definitions

No subgroup analyses will be conducted for final analysis.

# 1.5 Assessment windows, baseline and post baseline definitions, missing data handling

#### 1.5.1 Assessment windows

No assessment windows have been defined for this study. Visit windows are described below.

If not otherwise specified, 'first dose', 'randomization' and 'baseline' are with respect to extension.

## 1.5.2 Study Day 1 and other study days

Study day is defined with respect to extension. The first day of administration of randomized study treatment (first dose) in extension is defined as *Study Day 1* or *Day 1*.

All other study days will be labeled relative to Day 1. For event dates on or after Day 1, study day for a particular event date is calculated as [Date of event] – [Date of first dose]+1, i.e., Day 2, Day 3, etc., will be one day, two days, etc., after Day 1, respectively. For the dates before Day 1, study day for an event date is calculated as [Date of event] – [Date of first dose], i.e., Day -1, Day -2, etc., will be one day, two days, etc., before Day 1, respectively. Duration of an event will be calculated as (Event end date – Event start date + 1).

Novartis	Confidential	Page 17
RAP Module 3	9-Apr-2018 (1:15)	Secukinumab / AIN457A2302E1

The descriptor "Day 0" will not be used.

#### 1.5.3 Screening (extension), baseline and post-baseline definitions

*Screening* refers to any procedures (e.g., checking inclusion and exclusion criteria) performed prior to the date of first dose of study treatment (for safety analysis) or prior to the randomization date in extension (for efficacy analysis). Per protocol, subject informed consent must be obtained prior to performing any study related activity. The date of signing informed consent is the start date of screening period. Any assessment obtained during the screening period will be labeled screening assessment. Assessments made on Day 1 may occur before or after the randomization or the first dose in extension. Further information will be found in [RAP Module 8].

Baseline is defined with respect to core and extension as follows:

Core baseline:

For efficacy analyses, core baseline is the last assessment (including unscheduled visits) obtained before the randomization in core. All assessments obtained after randomization in core are considered as post-baseline unless otherwise specified.

For safety analyses, core baseline is the last assessment (including unscheduled visits) obtained before the first dose of study treatment in core. All assessments obtained after the first dose of study treatment in core are considered as post-baseline unless otherwise specified.

Of note, as core baseline measurements are already identified in the core studies, they can be readily used for the purpose of extension study.

Extension baseline:

For efficacy analyses, extension baseline is the last assessment (including unscheduled visits) obtained on or after Week 52 and before the randomization in extension. All assessments obtained after randomization in extension are considered as post-baseline unless otherwise specified.

For safety analyses, extension baseline is the last assessment (including unscheduled visits) obtained on or after Week 52 and before the first dose of study treatment in extension. All assessments obtained after the first dose of study treatment in extension are considered as post-baseline unless otherwise specified.

In general, a baseline value refers to the last measurement made prior to administration of the first dose of study treatment. However, for patient reported outcomes (e.g. patient's assessment of PSA pain), lab, ECG, if no pre-treatment value exists a value recorded after first dose can also be used as baseline if it was collected on the same day as first dose.

For efficacy analyses, core baseline will be used for PASI and IGA related variables, such as PASI response, PASI score, et al. Extension baseline will be used for PRO variables.

For safety analyses, extension baseline will be used for all safety variables if not specified.

